**12.8 \* Secondary Outcome(s)**

Indicate which **additional variable(s)** will be assessed to judge the secondary outcome(s). Give measurement units, if applicable.

Characterization of effector function of pathogen-specific IgGs during infection as a function of Fc glycan composition:

- The IgG subclass distribution will be determined using data resulting from the mass spec analysis performed for the primary study outcome.
- *In vitro* analysis of antibody dependent cell cytotoxicity and antibody dependent cellular phagocytosis mediated by anti-influenza IgG with different Fc glycan profiles.
- *In vitro* analysis of cellular maturation and function using PBMCs from study participants.
- Analysis of gene expression using PBMCs from study participants.
- *In vivo* analysis of protection mediated by anti-influenza or anti-pneumococcal IgG with different Fc glycan composition in murine influenza virus or pneumococcal models of infection.

**12.9 \* Methods and Procedures**

Please provide a description of the laboratory and clinical analyses and procedures that will be performed. Include the role of external collaborators and consultants when appropriate. Please refer to Help text for Guidance.

**Study Design:**

The study population consists of healthy volunteers between the ages of 18 and 80.

**215 volunteers who meet all the eligibility criteria will be enrolled in this study.**

The study is divided into 3 arms. The groups are defined as follows:

**Arm I: Age 18-64 group:** Groups of 10 study participants each (except for group 2 which includes 25 participants) < 65 years of age (< 50 years of age for Flumist vaccine and < 55 years of age for meningococcal vaccines) will be **vaccinated with one of seven FDA approved vaccines (85 participants total):** **Group 1)** Fluzone intradermal influenza virus vaccine, **Group 2)** Fluzone intramuscular influenza virus vaccine, **Group 3)** Pneumovax 23 (plain polysaccharide pneumococcal vaccine), **Group 4)** Prevnar/PCV13 (pneumococcal conjugate vaccine), **Group 5)** MPSV4 (plain polysaccharide meningococcal vaccine), **Group 6)** Mencevo (meningococcal conjugate vaccine), **Group 10)** Flumist Quadrivalent (intranasal influenza live vaccine).

**Arm II: Age 65-80 group:** Groups of 10 study participants ≥65 years of age will be **vaccinated with one of three of the FDA approved vaccines (30 participants total):** **Group 7)** Fluzone intramuscular influenza virus vaccine, **Group 8)** Pneumovax 23, **Group 9)** Prevnar. Meningococcal vaccines, the intradermal influenza vaccine and intranasal Flumist will not be administered to participants in Arm II.

**Arm III: Healthy adults, age 18-80, with a specific medical history as described here and in Section 12.11 (Inclusion Criteria):** Groups of 25 study participants will be vaccinated with the Fluzone intramuscular influenza virus vaccine (100 participants total). **Group 11)** Prior diagnosis of dengue fever or dengue virus infection. **Group 12)** Prior diagnosis of dengue hemorrhagic fever. **Group 13)** Prior diagnosis of chikungunya virus infection. **Group 14)** Prior diagnosis of zika virus infection

**The study will occur in four phases:**

**Phase 1:** Volunteers will be recruited to receive influenza vaccines (Groups 1, 2, 7, 10). Recruitment for Groups 1 and 7 will occur simultaneously and volunteers will be enrolled sequentially - enrollment into Group 1 will be given priority over Group 2 because the intradermal vaccine preparation for the 2012-13 influenza season will expire earlier than the intramuscular preparation (April 2013 vs. June 2013). Volunteers will be recruited to receive the Flumist influenza vaccine (Group 10) beginning fall of 2013.

**Phase 2:** Volunteers will be recruited to receive one of the pneumococcal vaccines (Groups 3, 4, 8, 9)

- these subjects will be recruited simultaneously and will be randomized to receive either the Pneumovax or Prevnar vaccines.

**Phase 3:** Volunteers will be recruited to receive one of the meningococcal vaccines (Groups 5 and 6) - these subjects will be recruited simultaneously and will be randomized to receive either the MPSV4 or Menveo vaccines.

**Phase 4:** Volunteers will be recruited for Arm III of the study to receive the Fluzone intramuscular vaccine (Groups 11-14)

Study participants will not be blinded. During the analysis phase, samples will be coded so that the precise vaccine administered within each phase is unknown.

Study visits will be scheduled as follows for groups 1-10: screening, day 0 (within 4 weeks of screen), day 7 safety visit, and weeks 3, 5, 7, 9, and 12. On Day 3-4, a telephone call will be made to check on subject's medical status.

Groups 11-14 will be scheduled as follows: day 0 (within 4 weeks of screen), day 7 safety visit, and week 3. We will not collect samples at weeks 5, 7, 9 or 12 for Groups 11-14 because our existing data on intramuscular Fluzone immunization from Group 2 demonstrate that the major Fc glycan modifications occur during the first 3 weeks following vaccination.

**We do not anticipate any safety issues related to this protocol as all vaccines to be used have been FDA approved and all study participants are healthy adults.**

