**12.12 \* Will samples be coded?**

Yes  No

If Yes, Please describe coding scheme consistent with GCP. If samples will not be coded, please provide justification for this proposed departure from GCP practice.

The blood samples for all volunteers will be coded using the IRB approval number, date, and subject number, e.g. TWA-0804-001. The subject codes will be maintained in a password-protected database

on a RUH backed-up computer in the [name] lab that is accessed only by the Principal Investigator and the research team.

Once the samples are processed, the plasma will be stored in a -80C freezer in the [name] lab until time of assay.

If available, upload the Data and Sample Sharing Management Plan approved by RU IT.

Version	Title	Category	Expiration Date	Document Outcome	Checked Out	View Document
---------	-------	----------	-----------------	------------------	-------------	---------------

No Document(s) have been attached to this form.

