**Recruitment Implementation:**

**Advertising-** CRROSS will place ads both in broadly distributed NY area newspapers (i.e Metro) as well as specific papers/platforms that are circulated among the target populations, namely individuals who have lived in or travel to areas with high rates of infection (i.e Caribbean Life, Caribbean American Weekly). The populations include individuals from the Dominican Republic, Puerto Rico, other Caribbean islands, and Brazil. Demographic data from ad vendors, and demographic mapping resources, such as [http://www.nytimes.com/interactive/2011/01/23/nyregion/20110123-nyc-ethnic-neighborhoods-map.html?\\_r=1&](http://www.nytimes.com/interactive/2011/01/23/nyregion/20110123-nyc-ethnic-neighborhoods-map.html?_r=1&) are used to target advertising efforts when possible. Other media outlets will include internet (Voices of NY, Craigslist, Clinicaltrials.gov, [centerwatch.com](http://centerwatch.com)), radio (i.e WBLS 107.5 FM), and others as appropriately identified. **Research Volunteer Repository** Database – The investigator has agreed to associate protocol TWA-0804 with RKO-0648, the Research Volunteer Repository Protocol, enabling the CRROSS to query the existing volunteer database to identify a list of potential volunteers who have agreed to be contacted for future studies and who meet basic eligibility criteria. The CRROSS will contact potential volunteer as allowed to determine interest and will refer eligible and interested volunteers to the study coordinator/investigator. In parallel, the research team will seek and document the granting or denial of permission to contact volunteers about future studies.

**Centralized Call Management** – CRROSS will work with the research team to develop a protocol-specific pre-screening script based on IRB approved protocol eligibility criteria to prescreen volunteers who call [name]. Potentially eligible candidates will be scheduled for the study team for further screening. CRROSS staff will also call volunteers based on Repository queries described above. Research teams are responsible to provide timely updates on pre/screening outcomes (through iRIS, etc.) to keep CRSO strategies on target.

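### The only masking rule hides the vaccine within each phase; visit, age group and Arm III infection history are not covered

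*Combined protocol and SAP*

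**What the plan says.** On blinding, the four-phases text of Section 12.9 says "Study participants will not be blinded", followed by the one masking rule: "During the analysis phase, samples will be coded so that the precise vaccine administered within each phase is unknown".

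Section 12.12 describes the label: "The blood samples for all volunteers will be coded using the IRB approval number, date, and subject number, e.g. TWA-0804-001". The code list is kept in a password-protected database on a laboratory computer, "accessed only by the Principal Investigator and the research team". The Blood Collection text in Section 12.9 adds that specimens go through a GLP processing laboratory and are identified by a code number alone.

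The comparisons are set out elsewhere. Section 12.10 tests day 0 against day 21 within participants. Section 12.7 lists route, age (below 65 versus 65 and over) and past flavivirus or alphavirus infection as factors to be assessed, using lectin blot and mass spectrometry. For Arm III the Study Design text states: "Groups of 25 study participants will be vaccinated with the Fluzone intramuscular influenza virus vaccine (100 participants total".

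**The concern.** A laboratory mask protects a comparison only if it hides the factor being compared. This one hides vaccine identity, whereas several of the main comparisons are between visits, age groups or infection histories.

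Lectin blot is one of the two primary measurement methods. I assume, as general laboratory experience and not from the documents, that blot exposure, background handling, repeat runs and acceptance of spectral peaks leave the reader some discretion. A reader who knows which sample is post-vaccination, or which participant had haemorrhagic dengue, can lean towards the expected answer without intending to. The expectation already exists: Section 12.9 reports that earlier Fluzone recipients showed Fc glycan changes after vaccination, mostly within three weeks.

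At stake is whether a pre-to-post shift, or a difference between infection groups, can be presented as measured blind.

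**Working it through.** The plan gives no figure to reproduce here. The check counts participants by phase and sets the masking rule against each planned contrast.

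**Inputs.** Group sizes come from the Study Design text of Section 12.9: 10 each in Groups 1 and 3 to 10, and 25 each in Groups 2 and 11 to 14. Phase membership comes from the four-phases text.

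**Participants and vaccines per phase**

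- Phase 1 (Groups 1, 2, 7, 10): 10 + 25 + 10 + 10 = 55; three influenza vaccines.
- Phase 2 (Groups 3, 4, 8, 9): 4 × 10 = 40; two vaccines.
- Phase 3 (Groups 5, 6): 2 × 10 = 20; two vaccines.
- Phase 4 (Groups 11 to 14): 4 × 25 = 100; one vaccine.
- Total: 55 + 40 + 20 + 100 = 215, which agrees with the stated enrolment.

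Phases with more than one vaccine hold 55 + 40 + 20 = 115 participants (115/215 = 53.5%). The single-vaccine phase holds 100 (100/215 = 46.5%).

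**Rule against contrasts**

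| Contrast | Factor to be hidden | Covered by the rule? | Participants |
|---|---|---|---|
| Vaccine or route within Phases 1 to 3 | Vaccine | Yes, nominally | 115 |
| Day 0 vs day 21 | Visit | No | All groups |
| Groups 2 vs 7, 3 vs 8, 4 vs 9 | Age group | No; same vaccine on both sides | 25 + 10 + 10 + 10 + 10 + 10 = 75 (34.9%) |
| Among Groups 11 to 14 | Infection history | No; one vaccine throughout | 100 |

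Aim 4 also involves adults without known infection. If Group 2 is that comparator (the text does not say so outright), it sits in Phase 1, so a rule that works within phases does not address the comparison.

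**Does the label hide visit anyway?** Section 12.12 puts a date in the code but does not define it. The printed example has no visible date: Section 17.1 shows that TWA-0804 is the protocol number ("The investigator has agreed to associate protocol TWA-0804 with RKO-0648"), so the example reads as protocol number plus subject 001. There are two readings:

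1. If the draw date is on the label, it puts each participant's tubes in order and shows which is post-vaccination.
2. If it is not, protocol and subject number cannot tell a day 0 tube from a day 21 tube. A further visit identifier must then exist that the plan does not describe.

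Neither reading documents a mask on visit.

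**Does the workflow need visit knowledge?** Section 12.11 sends only participants with a two-fold titre rise on to glycan analysis. Someone must therefore pair and order the pre- and post-vaccination samples before any blot is run. The plan does not say who does this, or whether the order is concealed again afterwards.

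**The case against.** The strongest reply is that Sections 12.9 and 12.12 may describe two different codes: a general specimen label, and a separate code applied for analysis. The documents do not exclude this. A reader might infer that the blind is bound to fail, but the text supports only that it is not shown to protect these contrasts.

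Three further inferences are tempting and do not stand.

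- **That the assay team holds the key.** The text says the research team. The laboratory name is redacted, personnel pages were removed, and the people who read blots and spectra are not identified.
- **That route group is visible.** Route is the vaccine difference within Phase 1, so the rule nominally covers it. It is true that "enrollment into Group 1 will be given priority over Group 2" and that the intranasal group starts in fall 2013, but exposure would need a draw date or sequential numbering on the label, or access to the key.
- **That the rule works only in Phases 2 and 3 (40 + 20 = 60 participants).** That counts where vaccine is randomised, not which contrasts are masked. On the text, vaccine is nominally masked for 115, and Phase 2 itself contains an unmasked age contrast.

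It is also fair to say that failing to state a mask on infection history is not the same as displaying it: the code alone is not shown to separate Groups 11 to 14. Mass spectrometry is a primary method too, and the documents give no size or direction of bias.

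These replies narrow the point. None of them supplies a mask for visit, age group or infection history.

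**Conclusion.** The point holds in a limited form. As written, the rule masks vaccine within phase and nothing else. It leaves out visit in the main paired comparison for every group, age group for 75 participants, and infection history for all 100 in Arm III. The plan also does not show that assay readers are separated from a label said to contain a date and subject number, or from a key open to the research team.

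The scope of the rule is read directly from the text and rests on no assumption. That bias could follow rests on two assumptions: that blot and spectral readings involve some reader judgement, and that no separate analysis code with wider scope exists. The amount of bias cannot be estimated from the documents. This should be corrected before the remaining assays are run; it does not show that existing results are biased.

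**What to change.** Amend the four-phases text of Section 12.9 and Section 12.12, for assays still to be run, as follows:

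1. Assay aliquots carry a random accession number with no date, subject number or visit.
2. The specimen-processing laboratory named under Blood Collection, or another person outside the assay team, assigns the numbers and holds the key.
3. That key-holder applies the two-fold titre criterion of Section 12.11 and releases accession numbers only, so responder selection does not reveal visit to the readers.
4. The mask covers vaccine, visit, age group and Arm III infection group.
5. Each participant's samples run in one batch in random order, with Groups 11 to 14 mixed across batches.
6. The key is released only after blot and mass-spectrometry quantities are locked.

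Group 2 samples already analysed need not be re-assayed. Any comparison of Arm III with those results should state how they were masked when read.

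The cost is relabelling, key-holder time for responder selection and batch lists, and a lookup request for each sample query. No extra participants, visits or blood are needed.

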#### **Protocol Timeline**

See Study Design groups 1-10 in other study documents

See Study Design groups 11-14 in other study documents

Subjects in Groups 1 and 2 (Fluzone ID < 65 years of age and Fluzone IM < 65 years of age) will be asked to return to the clinic for an additional study visit between 6 and 12 months from their Day of Vaccination (Day 0). This visit will include vital signs, any updates to their medical/vaccination history, as well as a blood draw of 23.5 ml for sera and PBMCs. The rationale to include this additional timepoint is that our data from subjects who received the 2012-13 Fluzone vaccines show modulations in Fc glycan composition on antigen-specific IgGs post vaccination; the Fc glycans change over time following vaccination, but are not at baseline composition by the 12 week timepoint (the latest timepoint) in our study. Inclusion of the 6-12 month timepoint in the Fluzone study groups will enable better characterization of the kinetics of Fc glycan changes, which is important since the modifications are likely to augment IgG effector functions. We will collect a detailed history of any vaccinations or illnesses occurring since the last study visit in order to incorporate the information into our analysis. Sera collected at this late timepoint will enable analysis of Fc glycan composition and PBMCs will enable analysis of vaccine-specific B and T cell functioning.

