**Weeks 3, 5, 7, 9, 12:**

- Vital signs (pulse, respiratory rate, blood pressure and temperature) will be taken.
- Research bloods (20-170mL) will be drawn.
- Perform a point of care pregnancy test for all female volunteers.
- Groups 11-14 will not have bleeds done at week 5,7,9,12 or thereafter.

During follow up visits at day 7 and weeks 3, 5, 7, 9 and 12, study participants will receive pregnancy testing prior to sample collection because pregnancy is known to alter Fc glycan composition and would thus significantly confound study results. Volunteers with positive pregnancy tests will be discontinued from further participation in the study.

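### The 6-12 month visit for Groups 1 and 2 lists no pregnancy test and has no rule for influenza re-exposure, so either could distort the late glycan kinetics

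*Combined protocol and SAP*

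**What the plan says.** Section 12.9, Protocol Timeline, adds one visit for Groups 1 and 2 (intradermal and intramuscular Fluzone, under 65). These participants "will be asked to return to the clinic for an additional study visit between 6 and 12 months from their Day of Vaccination (Day 0". The reason given is that glycans in the 2012-13 vaccinees "are not at baseline composition by the 12 week timepoint (the latest timepoint) in our study". The content is itemised: "This visit will include vital signs, any updates to their medical/vaccination history, as well as a blood draw of 23.5 ml", for serum and PBMCs. On intervening events, which it means to take into account when the data are analysed, the plan says: "We will collect a detailed history of any vaccinations or illnesses occurring since the last study visit in order to incorporate the information into our" [...].

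Section 12.9, Weeks 3, 5, 7, 9, 12, requires a pregnancy test before sampling at day 7 and at each of those weeks, "because pregnancy is known to alter Fc glycan composition and would thus significantly confound study results". It adds: "Volunteers with positive pregnancy tests will be discontinued from further participation in the study".

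On dates, section 9.6 gives initial IRB approval as 7 February 2013. The Phase 1 text in section 12.9 says that the 2012-13 intradermal preparation "will expire earlier than the intramuscular preparation (April 2013 vs. June 2013"), and that FluMist recruitment begins in fall 2013.

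For time courses, section 12.10 names repeated measures ANOVA, descriptive graphics and possibly fitted curves. It has no rule for participants who are re-vaccinated, infected or pregnant.

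**The concern.** The late visit supplies the only sample after week 12, so what the study can say about longer-term glycan kinetics rests on it. Two things could disturb that sample.

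The first is pregnancy. The protocol names it as a confounder and controls for it at every visit up to week 12. It then lists no such control at the one visit that follows a gap of months. An unrecognised pregnancy would enter the late data unnoticed.

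The second is renewed influenza exposure. The window is six months wide and is not tied to the participant's next influenza vaccination. A new vaccination or infection could restart the response whose decline is being followed. A history will find what participants report, but not infection that they did not notice or mention. With no rule written in advance, the use of the history would be decided after the data are seen.

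**Working it through.** **Inputs.** Expected change 10 points, SD 4.4, inflated SD 5.72, significance level 0.017, power 80%, 20% non-response and 10% drop-off (section 12.11). Group sizes 10 and 25 (section 12.9). Dates as given above.

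**The plan's own figure.** An exact paired t-test with difference 10, SD 4.4 × 1.30 = 5.72 and two-sided alpha 0.017 first reaches 80% power at n = 7 (power 0.86). Then 7/(0.8 × 0.9) = 9.7, so 10. The plan's n = 7 and n = 10 both reproduce. The inputs can be reused, and the point does not depend on the sample size.

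**Visit content.** The pregnancy test is listed at screening, day 0, day 7 and weeks 3, 5, 7, 9 and 12. It is not listed at 6-12 months. Up to week 12 the longest gap between visits after vaccination is 3 weeks (week 9 to 12). The gap to the late visit is about 26 − 12 = 14 weeks to 52 − 12 = 40 weeks.

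**Calendar for the 2012-13 vaccinees.**
- Earliest late visit: 7 February 2013 + 6 months = 7 August 2013.
- Latest: end April 2013 + 12 months = end April 2014 (intradermal); end June 2013 + 12 months = end June 2014 (intramuscular).
- With vaccination and visit dates assumed uniform, 98% (intradermal) and 99% (intramuscular) of the window falls on or after 1 September 2013. For 1 October the figures are about 90% and 95%.
- If Day 0 were instead in September to November (an assumption), only about 11% of the window would reach the following October and 25% the following September.

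**Size of a re-exposure effect (illustration).** Suppose a share p is re-exposed and undetected, each such participant carries the full 10-point shift, and everyone else is back at baseline.
- False mean residual = 10p.
- A mixture of 0 and 10 adds variance 100p(1 − p), so SE = √[(SD² + 100p(1 − p))/n].
- SD 4.4, n = 10, p = 0.1: √[(19.36 + 9)/10] = 1.68; 1/1.68 = 0.6 SE.
- SD 4.4, n = 10, p = 0.3: √[(19.36 + 21)/10] = 2.01; 3/2.01 = 1.5 SE.

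| p | False residual (points) | n=10, SD 4.4 | n=10, SD 5.72 | n=25, SD 4.4 | n=25, SD 5.72 |
|---|---|---|---|---|---|
| 0.1 | 1 | 0.6 SE | 0.5 SE | 0.9 SE | 0.8 SE |
| 0.2 | 2 | 1.1 SE | 0.9 SE | 1.7 SE | 1.4 SE |
| 0.3 | 3 | 1.5 SE | 1.3 SE | 2.4 SE | 2.0 SE |

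Simulation at SD 5.72 and a two-sided 5% level gives the chance of a significant but false difference from baseline. At n = 10 with 1, 2 or 3 re-exposed it is about 5%, 8% and 16%. At n = 25 with 2, 5 or 8 re-exposed it is about 7%, 24% and 55%. Both group sizes are upper limits, because section 12.11 restricts glycan analysis to participants with a two-fold titre rise.

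**The case against.** The strongest reply is that re-exposure has been foreseen. The plan collects a detailed vaccination and illness history for use in the analysis, so a reported vaccination or illness would be known. That stands. It narrows the gap to unreported infection and the absence of a rule.

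A reader might infer that re-exposure or pregnancy would simply pass for a persisting vaccine effect. The documents do not support this. Reported re-exposure is captured, and the protocol says that pregnancy alters Fc glycans without saying in which direction, so it could as easily resemble a return to baseline. A recognised pregnancy might also surface in the medical history update.

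A reader might also take a re-exposed share of 30-50%, divide 3-5 points by 4.4/√10 = 1.39, and obtain 2.2-3.6 standard errors. The documents give no such share, and that standard error leaves out the mixture variance. With it, the same shares give 3/2.01 = 1.5 to 5/2.11 = 2.4.

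Three further points stand:
- The visit also serves B and T cell analyses.
- It lies outside the day 0, 7 and 21 primary times (section 12.7) and outside the day 0 versus day 21 paired test (section 12.10).
- The window of the 2012-13 vaccinees has closed, since the text already includes an August 2018 amendment. Booking advice can help only visits still to come.

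Finally, the attached schedule of events is visible only for screening. The missing test is therefore established from the protocol text alone, although that text does itemise this visit.

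**Conclusion.** The point holds as a limited one. The protocol's own reason for pregnancy testing applies to the late sample, yet the listed content of that visit has no test; the two passages need to be reconciled. For the 2012-13 vaccinees the visit falls almost entirely after the next vaccination season has begun. Unreported infection is not looked for, and nothing states how the history will be used.

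The late kinetics could therefore be distorted, by an amount that the documents do not fix. With an undetected share of 10-30%, the illustration gives 1-3 points. That is minor at n = 10 and can matter at n = 25. It assumes that each re-exposed participant carries the full 10-point shift and that all others are at baseline. The effect of pregnancy is of unknown direction and is not quantified. The main day 0 versus day 21 comparison is not affected.

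**What to change.** 1. Reconcile the Protocol Timeline with the Weeks 3-12 text, so that the same point-of-care pregnancy test precedes the late draw. Leave samples from pregnant participants out of the kinetics estimate.
2. For visits still to be scheduled, prefer the early part of the window and, where feasible, a date before the participant's next influenza vaccination, without delaying that vaccination.
3. Pre-specify in section 12.10 that the main late-kinetics estimate uses participants with no reported influenza vaccination or illness and no titre rise from week 12 to the late visit, measured by ELISA on serum already drawn. Report all participants as a sensitivity analysis. Fix the size of rise that counts in advance. The two-fold threshold in section 12.11 is a candidate, but the plan uses it to select vaccine responders, not to detect re-exposure.

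Item 3 can still be applied to stored serum where visits are complete.

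The cost is protocol wording, one test already used at the other visits and one titre comparison. The booking window becomes narrower and a few samples are lost from one exploratory estimate. The titre check can also miss a boost that has been masked by waning since week 12.
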